6.2.5 Optional dose tapering strategy in the event of study drug discontinuation

Following interruption or discontinuation of ruxolitinib, symptoms of myelofibrosis may return over a period of approximately one week. There have been cases of patients discontinuing ruxolitinib who sustained more severe events, particularly in the presence of acute intercurrent illness. It has not been established whether abrupt discontinuation of ruxolitinib contributed to these events. Unless abrupt discontinuation is required, gradual tapering of the dose of ruxolitinib may be considered, although the utility of the tapering is unproven.

When a decision is made to permanently discontinue INC424 therapy for reasons other than low platelet counts or ANC levels, a dose tapering strategy may be considered, based on evaluation of the condition of the patient, current dosing regimen, and the clinical judgment of the investigator. If considered to be medically necessary, the investigator may use any treatment to manage withdrawal from INC424 including a gradual tapering of the study drug dosage or use of other medications to manage adverse drug reactions of discontinuation. Short-term courses of corticosteroids have been used to moderate the withdrawal of INC424 and may be considered as part of a tapering strategy. Corticosteroids may be started prior to, or concurrent with, INC424 tapering. When a decision has been made to discontinue the patient with utilization of a tapering strategy, regardless of the use of concomitant medications, safety data will continue to be assessed in accordance with the protocol until the end of INC424 administration and in the event of an AE through resolution of the AE.

6.2.6 Dose interruption and discontinuation of study drug

[figure not shown]
In some circumstances, it may be necessary to temporarily interrupt treatment as a result of adverse drug reaction that may have an unclear relationship to study drug. Except in cases of emergency or for protocol mandated holds for ANC or platelet count, it is recommended that the investigator consult with the Sponsor medical monitor (or other representative of the Sponsor) before temporarily interrupting therapy. Study drug may be held by the investigator at any time if there is concern about patient safety, and for all aspects of the conduct of the protocol the safety of the individual patient is paramount. Treating investigators may employ any means necessary to ensure patient safety, particularly in medical circumstances not anticipated by this protocol. Additionally, the investigator must obtain approval from the Sponsor before restarting study drugs that were temporarily discontinued for an adverse experience.

Dosing must be halted immediately if any of the following occur for patients starting with 15 & 20 mg BID:

- Platelet counts fall below 50,000/ μ L
- ANC levels fall below 500/ μ L
- Hemoglobin cannot be maintained \geq 6.5 g/dL despite the use of transfusion therapy

Dosing may be reinstated following dose holding using the re-start schema detailed in [Section 6.2.3](#). In order to provide sufficient data to make the dose adjustment decisions, it is recommended that hematology parameters be obtained at least weekly for platelet count $<$ 100,000/ μ L or ANC $<$ 1000/ μ L and at least two times weekly for platelet count $<$ 50,000/ μ L or ANC $<$ 500/ μ L. (Note: patients with platelet counts of $<$ 10,000/ μ L should be hospitalized, unless local or national practice does not permit it).

If a patient on a dose-hold requires frequent testing for safety parameters, these tests may be performed at a local laboratory. If the study drug is interrupted for any reason for more than 8 weeks, dosing may not be restarted, except in the case of splenectomy, for which a maximum 12 week period of study drug interruption is permitted. Although study guidelines provide for dose reduction/interruption for the management of hematologic or non-hematologic toxicities that occur during the course of the study, the following guidelines should be used to determine whether permanent discontinuation of study drug is necessary.

Discontinuation of study drug for hematologic toxicity:

Study drug MUST be permanently discontinued if the lowest allowed dose (5 mg BID or 5 mg QD with concomitant CYP3A4 inhibitor) is not tolerated due to the following:

- Platelets cannot be maintained $\geq 50,000/\mu\text{L}$.
- Absolute neutrophil count cannot be maintained $\geq 500/\mu\text{L}$.
- Hemoglobin cannot be maintained $\geq 6.5 \text{ g/dL}$ despite the use of transfusion therapy.

In the event that any patient permanently discontinues the study drug, regardless of reason, reasonable efforts should be made to have the patient return for an early termination visit and have the End of Treatment evaluations completed as described in [Section 7.6](#) and [Section 7.6.2](#). The site is requested to provide voluntary follow-up of all withdrawn patients, with regard to incidence of leukemia or death.

The date the patient discontinued the study drug and the specific reason for discontinuation will be recorded in the eCRF. This will include reasons such as discontinued due to disease worsening or withdrawn due to adverse event. This information will be used to summarize the reasons for study withdrawal.

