6.2.2 Dose interruption or dose reduction

For patients who do not tolerate the protocol-specified dosing schedule, dose adjustments are permitted in order to allow the patient to continue the study treatment. The following guidelines need to be applied: for all patients who are receiving INC424, there are mandatory dose decreases or dose interruptions for declining platelet counts or ANC levels that might be observed while on INC424 therapy. In addition to mandatory dose interruption or decrease for hematologic toxicities, there are mandatory criteria for permanent discontinuation of INC424 (See [Section 6.2.6](#)).

Dosing must be held if platelet counts decline below 50,000/ μ L (Grade 3 laboratory abnormality by CTCAE v. 3.0, or if ANC falls below 500/ μ L while receiving INC424.

6.2.2.1 Dose interruption or dose reduction for patients starting INC424 at doses of 15 – 20 mg p.o. BID

Doses should be decreased for platelet count values < 125,000/ μ L as shown in [Table 6-2](#) with optional restarting or resuming prior dose after recovery ([Section 6.2.3](#)). In order to provide sufficient data to make the dose adjustment decisions, it is recommended that hematology parameters be obtained at least weekly for platelet count <100,000/ μ L or ANC < 1000/ μ L and at least two times weekly for platelet count < 50,000/ μ L or ANC < 500/ μ L.

These changes must be recorded on the Dosage Administration Record eCRF.

Table 6-2 Dose reductions in INC424 for safety in patients with platelet count declines (for those starting on INC424 dose of 15 – 20 mg p.o. BID)

[figure not shown]
Platelet Count at Time of Decline	Dose at the Time of Platelet Decline				
	25 mg BID	20 mg BID	15 mg BID	10 mg BID	5 mg BID
Dose that MUST be Instituted					
≥ 125,000/ μ L	No dose reduction required				
100,000/ μ L to < 125,000/ μ L	20 mg BID	20 mg BID	15 mg BID	10 mg BID	5 mg BID
75,000/ μ L to < 100,000/ μ L	10 mg BID	10 mg BID	10 mg BID	10 mg BID	5 mg BID
50,000/ μ L to < 75,000/ μ L	5 mg BID	5 mg BID	5 mg BID	5 mg BID	5 mg BID
< 50,000/ μ L	Stop Dosing				

6.2.2.2 Dose interruption or dose reduction for patients starting INC424 at doses of 5 mg p.o. BID

Dose modifications are made according to the platelet count as follows (see [Table 6-3](#)):

- If platelets > 25,000 - < 50,000/ μ L: reduce the INC424 dose by 5 mg o.d.
- If platelets ≤ 25,000/ μ L: hold treatment. Treatment can be restarted at a later date if platelets increase to ≥ 50,000/ μ L.

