6.2.3 Restarting or reinstating previous dose

6.2.3.1 Restarting or reinstating previous dose for patients who start INC424 15 – 20 mg BID

Dosing of INC424 may be restarted or increased following recovery of platelet counts and/or ANC to acceptable levels as illustrated in [Table 6-4](#) for those patients who start on INC424 15 – 20 mg BID. The objective for restarting or escalating after a reduction for safety is to find the highest safe dose of INC424 for each patient, with increases in dose generally not more than in increments of 5 mg BID and not more often than every 2 weeks. Patients who are restarting after a reduction for thrombocytopenia may not receive doses above 20 mg BID maximum. Similarly, ANC levels that decline to < 500/ μ L necessitate immediate dose interruption ([Section 6.2.6](#)). ANC level recovery to 500 / μ L and above but less than 750/ μ L will allow dosing to be restarted at 5 mg BID, and ANC levels between 750/ μ L, but < 1000/ μ L may restart at 10 mg BID. Absolute neutrophil count level increases to above 1000/ μ L will allow a further dose increase to a maximum of 20mg BID.

The maximum dose used should never exceed 5mg BID LESS than any dose that resulted in platelets falling below 100,000/ μ L or ANC falling below 500/ μ L. After restarting using the guidelines in [Table 6-4](#), if it is found that a patient cannot tolerate the lowest allowed dose (5mg BID, or 5mg QD with concomitant CYP3A4 inhibitor, see [Section 6.2.4](#)) without platelets falling below 50,000/ μ L, neutrophils falling below 500/ μ L, or Hgb falling below 6.5g/dL despite the use of transfusion therapy, drug must be permanently discontinued ([Section 6.2.6](#), and [Section 7.6.1](#)).

Table 6-4 **Restarting or increasing INC424 dose after safety interruptions or dose reductions for patients starting on doses of 15 – 20 mg BID**

Current Platelet Count	Dose Restart or Dose Increase Guidelines
< 50,000/ μ L	Continue hold
50,000/ μ L to < 75,000/ μ L	5 mg BID for at least 2 weeks; if stable, may increase to 10 mg BID
75,000/ μ L to < 100,000/ μ L	10 mg BID for at least 2 weeks; if stable, may increase to 15 mg BID
100,000/ μ L to < 125,000/ μ L	15 mg BID
\geq 125,000/ μ L	20 mg BID
Current ANC Level	Dose Restart or Dose Increase Guidelines
< 500/ μ L	Continue hold
500 to < 750/ μ L	5 mg BID for at least 2 weeks; if stable, may increase to 10 mg BID
750 to < 1000/ μ L	10 mg BID for at least 2 weeks; if stable, may increase to 15 mg BID

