1000 to < 1500/ μ L	15 mg BID for at least 2 weeks; if stable may increase to 20 mg BID
\geq 1500/ μ L	20 mg BID

NOTE: Whether the dose interruption occurred because of neutropenia, thrombocytopenia or both, when restarting, both the platelet count and ANC must be considered to determine the restart dose, with the lower calculated dose being used.

6.2.3.2 Restarting or reinstituting previous dose for patients who start INC424 at 5 mg BID

Dosing of INC424 may be restarted or increased following recovery of the platelet count to $\geq 50,000/\mu\text{L}$. Reinitiate treatment at a dose of 5 mg o.d. The dose may be increased by 5 mg o.d. every two weeks based on platelet counts and the absence of other adverse events.

When the ANC is $< 500/\mu\text{L}$, hold INC424 dosing. INC424 can be reinitiated in this population once the ANC is $\geq 500/\mu\text{L}$, at a dose of 5 mg o.d. The dose may be increased by 5 mg o.d. every two weeks based on platelet counts and the absence of other adverse events.

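### The hemoglobin halt in Protocol 6.2.6 leads to a restart schema with no hemoglobin criterion, and it is worded only for 15 and 20 mg BID starters

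*Protocol*

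**What the plan says.** Protocol Section 6.2.6 introduces the halt with "Dosing must be halted immediately if any of the following occur for patients starting with 15 & 20 mg BID" and lists three triggers: platelets below 50,000/µL, ANC below 500/µL, and hemoglobin that cannot be held at or above "6.5 g/dL despite the use of transfusion therapy". One sentence then covers the way back for all three: "Dosing may be reinstated following dose holding using the re-start schema detailed in" Section 6.2.3.

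Section 6.2.3.1, for 15 and 20 mg BID starters, opens with "Dosing of INC424 may be restarted or increased following recovery of platelet counts and/or ANC to acceptable levels as illustrated in" Table 6-4. The table has five platelet rows and five ANC rows. Its note speaks of interruptions for neutropenia, thrombocytopenia or both, and says "when restarting, both the platelet count and ANC must be considered to determine the restart dose, with the lower calculated dose being used". The cap in the same section reads "The maximum dose used should never exceed 5mg BID LESS than any dose that resulted in platelets falling below" 100,000/µL, or ANC falling below 500/µL. Hemoglobin appears in 6.2.3.1 once, as a ground for permanent discontinuation if the lowest allowed dose is not tolerated after restart.

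Section 6.2.2 describes, for all patients, "mandatory dose decreases or dose interruptions for declining platelet counts or ANC levels that might be observed" on therapy, and adds that 6.2.6 holds mandatory criteria for permanent discontinuation. For 5 mg BID starters, Sections 6.2.2.2 and 6.2.3.2 and Table 6-3 give platelet and ANC rules and no hemoglobin hold.

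**The concern.** A mandatory halt needs a matching route back. Here one of the three triggers is sent to a schema that does not use it. Two sites following the text could restart similar patients at different times and doses after severe anemia, and the schema can name a dose above the one that was stopped. The protocol calls anemia dose related (Section 1.3.5). It also reports there that, where the phase III protocols gave no dose-reduction guidance for anemia, some investigators reduced the dose on their own initiative.

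This is first a safety matter. It also touches the reporting, because exposure after a halt feeds the primary adverse event incidence (Protocol 11.5.1, SAP 3.4.1), dose intensity (SAP 3.2), adverse events leading to dose adjustment (SAP 3.5.1) and transfusion status (SAP 3.6).

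**Working it through.** The plan gives no figure to reproduce, so the check sets the rules side by side and then runs Table 6-4.

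**1. Which parameter each rule uses**

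| Rule | Platelets | ANC | Hemoglobin |
|---|---|---|---|
| Immediate halt, 15 and 20 mg BID starters (6.2.6) | yes | yes | yes |
| Recovery condition for restart (6.2.3.1) | yes | yes | none |
| Restart dose (Table 6-4 and note) | yes | yes | none |
| Cap after toxicity (6.2.3.1) | yes | yes | none |
| Hold, 5 mg BID starters (6.2.2.2, 6.2.3.2, Table 6-3) | yes | yes | none |
| Permanent stop at lowest allowed dose (6.2.6, 7.6.1) | yes | yes | yes |

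**2. What Table 6-4 assigns.** The restart dose is the lower of the platelet-based and ANC-based doses. Crossing five platelet bands with five ANC bands gives 25 cells. The cells with both parameters at or above each successive band number 25, 16, 9, 4 and 1. The initial instruction is therefore:
- continue hold: 25 − 16 = 9 cells
- 5 mg BID: 16 − 9 = 7 cells
- 10 mg BID: 9 − 4 = 5 cells
- 15 mg BID: 4 − 1 = 3 cells
- 20 mg BID: 1 cell (platelets ≥125,000/µL and ANC ≥1500/µL)

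The result is identical at hemoglobin 5.0, 6.0, 6.4 and 7.0 g/dL, because hemoglobin is not an input. These are combinations of bands, not proportions of patients.

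**3. A patient halted for hemoglobin alone.** Such a patient has platelets of at least 50,000/µL and ANC of at least 500/µL, since otherwise another trigger would also apply. That leaves the 16 non-hold cells, and each names a dose with no hemoglobin condition.

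**4. Top-cell dose against the halted dose.**
- Halted at 15 mg BID: 20/15 = 1.33
- Halted at 20 mg BID: 20/20 = 1.00
- Halted at 25 mg BID: 20/25 = 0.80

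The first case can occur. Section 6.1.1 starts patients with 100,000 to 200,000/µL platelets at 15 mg BID, so a count of 125,000/µL or more is within their entry range. A move from 15 to 20 mg BID is a single 5 mg BID step, so the general step limit in 6.2.3.1 does not exclude it. The ordinary Week 4 increase (6.2.1.1.1) asks for platelets above 150,000/µL and never lower on drug, a spleen reduction under 40%, and ANC held at 1000/µL or more. The top cell of Table 6-4 has a lower platelet bar and no spleen condition, though a higher bar for the current ANC.

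**5. Patients starting at 5 mg BID.** Section 6.2.1.2 allows escalation under a ceiling of 25 mg BID. Above the lowest allowed dose, no mandatory temporary hemoglobin hold is written for them.

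**The case against.** The strongest reply is that other text limits the effect. Section 6.2.6 requires Sponsor approval before restarting drug that was stopped for an adverse experience, and Section 9.1.2.1 treats a protocol-required hold for a laboratory abnormality as an adverse event. Consultation with the medical monitor is also recommended before an interruption, and only emergencies and mandated platelet or ANC holds are exempt. Reinstatement is permissive, the rows of Table 6-4 are guidelines, and increases should generally be at least two weeks apart. The study is single-arm and descriptive, and no bias in any estimate has been shown.

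All of this stands, and it rules out some stronger readings. A reader might infer that a patient halted for hemoglobin qualifies at once for full dose. The documents do not support that: approval is needed, 20 mg BID is one cell of 25, and the study maximum is 25 mg BID. A reader might also infer that the halt has no effect. It applies again for as long as hemoglobin still cannot be maintained.

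The gap remains all the same. The approval step supplies neither a hemoglobin criterion nor a dose, whereas platelet and ANC holds have explicit rows as well as the same approval step.

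**Conclusion.** The point holds as a cross-reference that does not work for one of its three triggers. For a hemoglobin-only halt, the schema states no hemoglobin recovery condition and assigns a dose from platelets and ANC. In the top cell that dose is 1.33 times a halted 15 mg BID dose, subject to Sponsor approval. This rests on reading 6.2.6 as sending all three triggers to 6.2.3, which is its plain wording.

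The second limb also holds: the mandatory temporary halt is worded only for 15 and 20 mg BID starters. It would be too much to infer that 5 mg BID starters are unprotected. Permanent discontinuation at the lowest allowed dose covers them (6.2.6, and 7.6.1, which names low-platelet patients), and the investigator may hold drug at any time for safety. What they lack is a mandatory temporary hold, chiefly after escalation.

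The number of patients affected cannot be derived. Grade 3/4 anemia in 45.2% of the placebo-controlled phase III trial (Section 1.3.5) may look like the size of the problem, but it counts all such anemia and not this trigger. Dose reduction or interruption for anemia in 5.6% of pooled phase III patients (same section) is not this trigger either.

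**What to change.** The sponsor should reconcile Sections 6.2.2, 6.2.3 (Table 6-4, its note and the dose cap), 6.2.6 and 7.6.1 on two matters:
- The restart route for a hemoglobin hold should take hemoglobin into account.
- The sections should agree on whether the hemoglobin halt covers patients who started at 5 mg BID.

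The clinical values are for the sponsor's medical team to set, and none is proposed here. The cost is text only. Section 12.11 requires a written amendment for any change, and an investigator letter can announce it. No new data are needed, since hemoglobin is already part of the hematology panel (Section 8.2.9).

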6.2.6.1 Dose reduction for non-hematological safety

Study drug MUST be permanently discontinued upon the occurrence of a clinically significant Grade 3 or Grade 4 laboratory or non-laboratory abnormality attributed to ruxolitinib if fails to resolve to Grade 2 or better within 8 weeks or if a lower re-start dose or administration schedule is either not available or likely to be clinically ineffective.

[figure not shown]
Although study guidelines provide for dose reduction/interruption for the management of hematologic or non-hematologic toxicities that occur during the course of the study, the investigator should determine whether permanent discontinuation of study drug is necessary.

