6.2.4 Dose reductions for concomitant CYP inhibitor usage

INC424 is metabolized in the liver by the cytochrome (CYP) P450 metabolizing enzyme system, predominantly by the 3A4 isoenzymes. With concomitant dosing of strong (potent) CYP inhibitors such as oral ketoconazole, plasma exposure of INC424 increases approximately 2-fold. Thus, a dose reduction of $\sim 50\%$ for INC424 is appropriate for patients who take ketoconazole or other potent CYP3A4 inhibitors as concomitant medication. Twice daily (BID) doses will be decreased to the corresponding once daily dose as follows:

- If dose is 25 mg BID, change dose to 25 mg **QD**
- If dose is 20 mg BID, change dose to 20 mg **QD**
- If dose is 15 mg BID, change dose to 15 mg **QD**
- If dose is 10 mg BID, change dose to 10 mg **QD**
- If dose is 5 mg BID, change dose to 5 mg **QD**

If a patient is already on a once daily dose of INC424, and a potent CYP3A4 inhibitor is added as a concomitant medication, the dose should be reduced to 5 mg every other day.

More frequent monitoring of hematology parameters and clinical signs and symptoms of ruxolitinib related adverse reactions is recommended upon initiation of a strong (potent) CYP3A4 inhibitor.

Potent inhibitors of CYP3A4 include oral ketoconazole, clarithromycin, itraconazole, voriconazole, nefazodone, telithromycin ([Flockhart 2007](#)). Based on the very low overall bioavailability of topical ketoconazole, no dosage adjustment is needed for use with topical ketoconazole. NOTE: once the course of therapy using a CYP 3A4 inhibitor has been completed, the patient should resume their prior BID dose regimen of INC424 beginning the next day.

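### At 5 mg BID with no lower regimen available, Protocol 6.2.6.1 mandates a permanent stop for drug-attributed Grade 3/4 non-hematologic toxicity that 7.6.1 exempts, makes optional or omits

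*Protocol*

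**What the plan says.** Protocol 6.2.6.1 sets the rule for non-hematologic toxicity: "Study drug MUST be permanently discontinued upon the occurrence of a clinically significant Grade 3 or Grade 4 laboratory or non-laboratory abnormality". The abnormality must be attributed to ruxolitinib, and one of two conditions must hold. Either it has not improved to Grade 2 or better within 8 weeks, or the second condition applies: "if a lower re-start dose or administration schedule is either not available or likely to be clinically ineffective". The section lists no exempt events. It closes by saying that "the investigator should determine whether permanent discontinuation of study drug is necessary". The parent section, 6.2.6, has a sentence with the same opening that ends differently: "the following guidelines should be used to determine whether permanent discontinuation of study drug is necessary".

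The floor dose is given in 6.2.6 under hematologic toxicity, where the drug must stop if "the lowest allowed dose (5 mg BID or 5 mg QD with concomitant CYP3A4 inhibitor) is not tolerated due to the following"; 6.2.3.1 gives the same floor for patients who started at 15–20 mg BID.

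Protocol 7.6.1 introduces its safety withdrawals as the 6.2.6 criteria, spelled out. For non-hematologic toxicity at the lowest dose it lists two triggers: a related, clinically significant Grade 4 laboratory abnormality, and a Grade 4 clinical event that recurs on re-challenge. Each carries a list of exemptions. It then says drug may be stopped, at the investigator's option, for a Grade 4 clinical event not confirmed on rechallenge. Section 6.2.2.2 repeats that optional sentence.

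**The concern.** A mandatory stopping rule for serious drug-attributed toxicity should give one answer. Here a site reading 7.6.1 can keep on drug a patient whom 6.2.6.1 says must stop, and neither section says which governs. The study's primary objective is safety, so the handling of these patients matters in itself. The decisions also feed the summary of AEs leading to study drug discontinuation in SAP 3.4.1.2.

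The likely cause is incomplete harmonization. The Amendment 5 change list has 35 numbered items. Item 17 creates 6.2.6.1, and none names 7.6.1 or 6.2.2.2.

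**Working it through.** No arithmetic beyond counting applies, so the sections are set side by side.

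**Step 1: the patient in whom the comparison is firm.** Take someone who started at 15–20 mg BID and is now at 5 mg BID. Lower regimens exist only in special situations:
- With a potent CYP3A4 inhibitor (6.2.4), 5 mg BID becomes 5 mg once daily. For a patient already dosed once daily when the inhibitor is added, "the dose should be reduced to 5 mg every other day".
- With a dual CYP2C9/CYP3A4 inhibitor (6.3.2), the dose is cut by about half.
- With severe renal impairment (6.2.2.3) or hepatic impairment (6.2.2.4), the dose is or may be reduced.

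Outside these situations no lower re-start dose is available, and the second condition of 6.2.6.1 is met. Patients who started at 5 mg BID are set aside: Table 6-3 and 6.2.3.2 give them a 5 mg once-daily step. The optional sentence in 6.2.2.2 sits under that group and decides none of the cases below.

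**Step 2: compare the rules for that patient.** Every event is clinically significant and attributed to drug.

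| Event | 6.2.6.1 | 7.6.1 | Result |
|---|---|---|---|
| 1. Grade 3 laboratory | must stop | not listed | gap |
| 2. Grade 3 clinical | must stop | not listed | gap |
| 3. Grade 4 clinical, not confirmed on rechallenge | must stop | may stop | conditional conflict |
| 4. Recurrent Grade 4 clinical, exempt list | must stop | not required | conflict |
| 5. Grade 4 laboratory, exempt list | must stop | not required | conflict |
| 6. Grade 4 laboratory, not exempt | must stop | must stop | agree |
| 7. Recurrent Grade 4 clinical, not exempt | must stop | must stop | agree |

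Of seven event types, two conflict clearly, one conflicts conditionally, two are gaps and two agree (2 + 1 + 2 + 2 = 7).

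**Step 3: case 3.** Suppose the event occurs at 10 mg BID, drug is held, and 5 mg BID is then tolerated. A lower dose was available, so that branch of 6.2.6.1 is not triggered and the option in 7.6.1 is compatible with it. Suppose instead that the event first occurs at 5 mg BID. Then 6.2.6.1 requires a stop and leaves no room for rechallenge, while 7.6.1 makes stopping optional if its sentence covers patients never rechallenged at a lower dose.

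**Step 4: count the exemptions in 7.6.1.** Laboratory: serum iron, total bilirubin, triglycerides, total cholesterol and HDL cholesterol = 5. Clinical: fatigue, insomnia, obesity, disabling constitutional symptoms that do not threaten life, salivary gland changes, arthritis and joint effusion = 7. Total 5 + 7 = 12, against none in 6.2.6.1. Of the five laboratory tests only bilirubin is in Appendix III. The other four can arise only if a site measures them anyway, but a clinically significant result would still be an AE under 9.1.1.

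**The case against.** Several arguments on the other side have force.

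- **Grade 3.** A reader might infer that 7.6.1 allows treatment to continue after a Grade 3 event. It does not say so. It refers to the 6.2.6 criteria, and 6.2.6.1 is a subsection of 6.2.6, so a Grade 3 stop is reachable by cross-reference. Silence is a gap, not permission. This stands.
- **First Grade 4 clinical event.** A reader might infer that this always conflicts. Step 3 shows a consistent reading when rechallenge took place at a lower dose. This stands as a limit on case 3.
- **Last sentence of 6.2.6.1.** It might be taken to cancel the mandatory stop. It can also be read as letting the investigator stop even where reduction is allowed. Both readings are open. The contrast with the parent sentence in 6.2.6 makes the discretionary one plausible, but the text does not settle it.
- **Study withdrawal versus drug discontinuation.** The glossary separates them. That does not resolve the mismatch: 7.6.1 presents its list as the drug-discontinuation criteria, and its optional sentence concerns study drug.
- **Other controls.** After a hold, "the investigator must obtain approval from the Sponsor before restarting study drugs that were temporarily discontinued for an adverse experience"; and 7.6.1 requires a stop when the investigator judges that continuing would harm the patient. A site can also satisfy both sections by following the stricter one. These limit the problem, but the first applies only to restarts, the second is discretionary, and nothing names the stricter rule as governing.

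**Conclusion.** The inconsistency is real and is in the current text, but it is narrow. It is a clear conflict for exempted recurrent Grade 4 clinical events and exempted Grade 4 laboratory abnormalities. It is a conflict for an unconfirmed Grade 4 clinical event only if there was no rechallenge at a lower dose. For Grade 3 it is an omission. The last sentence of 6.2.6.1 adds ambiguity.

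This rests on the patient having started at 15–20 mg BID, being at 5 mg BID, and having no inhibitor or organ-impairment reduction that opens a lower regimen. Whether the 8-week condition also covers an event that persists while dosing continues is a matter of interpretation; no conflict is claimed there.

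A reader might infer a material effect on the trial's results. The documents do not support that. They record 2238 patients enrolled but not how many were at 5 mg BID, or still on drug, when Amendment 5 took effect, so no count can be derived. No effect on the primary endpoint, the incidence of treatment-emergent AEs, can be shown. What remains is inconsistent handling of the same toxicity and possibly a small effect on the discontinuation table.

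**What to change.** The text is wrong as written and can be corrected by amendment wording, with no new assessments:

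1. State that 6.2.6.1 governs permanent discontinuation for non-hematologic toxicity.
2. In 7.6.1, replace the non-hematologic bullets and the optional sentence with a reference to 6.2.6.1. Point the optional sentence in 6.2.2.2 there too.
3. Reword the last sentence of 6.2.6.1 to: *The investigator applies these criteria and may discontinue study drug earlier.*

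If the sponsor wants to keep the 7.6.1 exemptions, move all 12 unchanged into 6.2.6.1: Grade 4 only, with the direct-bilirubin and Grade 3 creatinine qualifiers. Limit them to the branch where no lower dose is available, so that the 8-week non-resolution stop stays mandatory. Extending any exemption to Grade 3 would be a medical decision for the sponsor and is not part of this fix.

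The cost is possibly a few more mandatory stops at the lowest dose. Those patients face the return of symptoms described in 6.2.5, which already offers optional tapering.
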